10.2. Pharmacokinetic Variables

Where possible, the following PK parameters will be determined for verinurad, its metabolites M1 and M8, allopurinol and oxypurinol using plasma concentrations for Treatment Period 1 (reference treatment), Treatment Period 2 (test treatment 1) and Treatment Period 3 (test treatment 2).

10.2.1. Plasma Parameters

Primary PK parameters

Cmax	Maximum observed plasma peak concentration
AUCinf	Area under plasma concentration-time curve from time zero to infinity
AUClast	Area under the plasma concentration-time curve from zero to time of last quantifiable concentration

Secondary PK parameters

AUC(0-24)	Area under plasma concentration-time curve from zero to 24 hours post-dose
tmax	Time to reach peak or maximum observed concentration following drug administration
t½λz	Half-life associated with terminal slope (λz) of a semi-logarithmic concentration-time curve
λz	Terminal elimination rate constant
CL/F	Apparent total body clearance of drug from plasma after extravascular administration (parent drug only)
MRTinf	Mean Residence Time of the unchanged drug in the systemic circulation
Vss/F	Volume of distribution (apparent) at steady state following extravascular administration (parent drug only)
Vz/F	Apparent volume of distribution during the terminal phase after extravascular administration (parent drug only)
MRCmax	Ratio of metabolite Cmax to parent Cmax
MRAUCinf	Ratio of metabolite AUCinf to parent AUCinf
MRAUClast	Ratio of metabolite AUClast to parent AUClast

Diagnostic PK Parameters

The following diagnostic parameters for plasma PK analysis will apply:

tlast	Time of last observed (quantifiable) concentration
λz lower	Lower (earlier) t used for λz determination
λz upper	Upper (later) t used for λz determination
λzN	Number of data points used for λz determination
λz span ratio	Time period over which λz was determined as ratio of t½λz
Rsq-adj	Statistical measure of fit for the regression used for λz determination adjusted for the number of used data-points (n obs)
AUCextr	Extrapolated area under the curve from tlast to infinity, expressed as a percentage of AUCinf

10.2.2. Calculation or Derivation of Pharmacokinetic Parameters

Pharmacokinetic parameters will be derived from the plasma concentration data for verinurad, M1, M8, allopurinol and oxypurinol using non-compartmental methods with Phoenix® WinNonlin® Version 8.1, or higher. All descriptive and inferential statistical computations will be performed using SAS® Version 9.3, or higher.

The PK parameters are calculated/estimated according to AZ standards [19].

Pharmacokinetic analysis for each analyte will, where data allows, be carried out using actual times determined from the PK sampling and dosing times recorded in the database. If actual times are missing, nominal times may be used.

- 10.3. Pharmacodynamic variable(s) Not Applicable
- **10.4.** Pharmacogenetics Not Applicable

11. STATISTICAL METHODS AND SAMPLE SIZE DETERMINATION

11.1. Description of the Analysis Sets

11.1.1. Enrolled Set

The enrolled set will consist of all subjects who were enrolled and assigned to treatment.

11.1.2. Safety Analysis Set

The safety analysis set will include all subjects who received at least the dose of verinurad+allopurinol in Treatment Period 1 and for whom any safety post-dose data are available.

Unless otherwise stated, the safety analysis set will be used for the presentation of all demographic and disposition data, as well as all safety analyses. Exposure to IMP will also be presented using the safety analysis set.

11.1.3. Pharmacokinetic Analysis Set

The PK analysis set will include all subjects in the Safety Analysis Set who receive verinurad+allopurinol dose and who have at least 1 quantifiable post-dose plasma concentration. In case of an important protocol deviation or event, affected PK data will be excluded from the descriptive and inferential statistical analyses, but will still be included in the study result listings.

Data for a subject may be excluded from the descriptive and inferential statistical analyses as a result of the following:

- Where a subject experienced vomiting at or before median tmax.
- Where the pre-dose concentration for an analyte is > 5% of Cmax in a specific PK sampling period

The exclusion of any subjects or time points from the calculation of the PK parameters will be documented by the PK Scientist including the reason(s) for exclusion.

The available concentration data and PK parameter data for any subjects excluded from the PK analysis set will be listed only. Concentration data for subjects excluded from the PK analysis set will be presented in the individual figures of concentration versus time plots.

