1.1.1.1. Clinical Pharmacokinetics

Following administration of verinurad as an extended-release capsule formulation (ER8), Cmax occurred 4 hours after dosing. Food did not affect verinurad exposure except for a 2-hour increase in time to maximum plasma concentration (tmax). The degree of protein binding of verinurad in human plasma was 97%. Glucuronidation is the major metabolic pathway of verinurad with oxidation as the minor pathway. The major metabolites observed in humans after oral verinurad dosing are the acyl glucuronides M1 and M8 which are renally cleared. The amount of verinurad in urine is small (<2% of given dose). The terminal half-life (t½) of verinurad was 13 hours in subjects with normal renal function and 21 hours in those

with moderate renal impairment. The exposure ([AUC] and Cmax) of verinurad increased in a dose proportional manner and the accumulation was minimal after once daily dosing. Subjects with an eGFR of 45 and 60 mL/min/1.73m² are predicted to have a 1.4 and 1.2-fold higher verinurad exposure, respectively, compared to those with normal renal function (eGFR of 90 mL/min/1.73m²). Asian subjects are predicted to have about 44% higher exposure compared to non-Asians after accounting for differences in renal function and body weight.

Further information on PK findings (including PK parameters of the verinurad IR formulation) is available in the IB [1].

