2. STUDY OBJECTIVES

2.1. Primary Objectives

Table 2-1 Primary Objectives and Outcome Measures

Primary Objectives	Outcome Measures
To assess the effect of a single dose of cyclosporine on the PK of verinurad	Verinurad Cmax, AUCinf and AUClast ratios of geometric means of test treatment (verinurad+allopurinol with cyclosporine), relative to reference treatment (verinurad+allopurinol alone).
To assess the effect of a single dose of rifampicin on the PK of verinurad	Verinurad Cmax, AUCinf and AUClast ratios of geometric means of test treatment (verinurad+allopurinol with rifampicin), relative to reference treatment (verinurad+allopurinol alone).

See List of Abbreviations for definition of abbreviations in Table 2-1

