- Blood samples will be taken at the following time points: up to 30 minutes pre-dose and at 30 minutes and 1, 1.5, 2, 3, 4, 5, 6, 8, 10, 12, 24, 36, 48, 72 and 96 hours post-dose.

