3.2.2. Dose Rationale

A single dose of 7.5 mg verinurad, formulated as an extended release capsule (ER8) is selected for this study. This is the middle dose currently tested in a Phase 2b study. The AUC and Cmax of verinurad increases in a dose proportional manner after administration of single doses of 4.5 to 12 mg ER8 verinurad capsule. Multiple dosing of 24 mg ER8 verinurad once daily doses, and single doses of 40 mg verinurad as immediate release tablets, have been assessed previously in healthy volunteers and been found to be well tolerated.

A single dose of 300 mg of allopurinol was selected because it is the intended clinical dose in the verinurad+allopurinol fixed-dose-combination.

A single dose of 600 mg cyclosporine reflects daily doses in transplant patients and has been used in similar drug-drug interaction studies in the past [12, 13].

A single dose of 600 mg rifampicin is the highest daily recommended dose and has been used for both single and multiple dosing in drug-drug interaction studies in the past [14, 15].

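### Does the vomiting exclusion at median tmax leave the primary verinurad AUC ratios unprotected?

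*Combined protocol and SAP*

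**What the plan says.** Section 11.1.3 (Pharmacokinetic Analysis Set) has three relevant layers.

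- A general clause, worded as mandatory, removes PK data affected by an important protocol deviation or event from descriptive and inferential analyses. It has no time limit.
- Two listed grounds follow, worded as discretionary. The first is "Where a subject experienced vomiting at or before median tmax". The second concerns a pre-dose concentration above 5% of Cmax and is framed by analyte and by PK sampling period.
- The PK Scientist documents every exclusion with its reason.

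Section 10.2.1 defines tmax only for the individual profile: "Time to reach peak or maximum observed concentration following drug administration". No median is defined. Under Section 10.2, "Where possible, the following PK parameters will be determined for verinurad, its metabolites M1 and M8, allopurinol and oxypurinol", in each of three treatment periods.

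For verinurad itself, Section 3.2.2 says the dose is "formulated as an extended release capsule (ER8) is selected for this study", and Section 1.1.1.1 states: "Following administration of verinurad as an extended-release capsule formulation (ER8), Cmax occurred 4 hours after dosing". The primary measures in Section 2.1 are "Verinurad Cmax, AUCinf and AUClast ratios of geometric means of test treatment" relative to verinurad plus allopurinol alone.

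**The concern.** The wording is open in two ways.

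First, the median has no owner. Five analytes in three periods give 15 possible study medians, and a historical value would also fit. A study median would have to be known when the analysis sets are settled before database hard lock.

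Second, a cutoff at the peak suits Cmax better than AUC. An extended-release capsule may still be delivering drug at the peak, so a subject who vomits later could lose part of the dose without meeting the listed criterion. By the definition of a median, up to about half the subjects may peak after the cutoff.

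If such a profile were analysed as a full dose, a loss in a test period would lower that ratio, and a loss in Treatment Period 1 would raise both. With about 12 evaluable subjects in an open-label study, one profile carries some weight, and a decision taken case by case is less comfortable than a fixed rule.

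**Working it through.** **Plan's own figure.** Section 11.4 gives an intra-subject CV of 24%, 12 subjects and a 90% interval within 1.58 to 2.53 around a ratio of 2, with 80% probability.

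- σ² = ln(1 + 0.24²) = 0.0560, so σ = 0.2366.
- Log half-width with normal quantiles: (1.645 + 0.842) × 0.2366 × √(2/12) = 0.240, giving limits of 1.57 to 2.54. This agrees closely with the plan.
- The stated limits correspond to ln(2.53/2) = 0.235, used below as the yardstick.

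**Share of the dose unabsorbed at 4 h.** Inputs from Section 1.1.1.1: peak at 4 h, and the half-life "of verinurad was 13 hours in subjects with normal renal function". Assume one compartment with first-order absorption.

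- ke = ln 2 / 13 = 0.0533 per h.
- tmax = ln(ka/ke)/(ka − ke) = 4 has the solution ka = 0.695 per h. Check: ln(0.695/0.0533)/(0.695 − 0.0533) = 4.0.
- Unabsorbed share = exp(−ka·t): 6.2% at 4 h and 0.02% at 12 h.

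**Effect on a primary ratio.** Suppose one of 12 subjects expels all remaining drug in a test period, a share L of the dose.

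- Ratio factor = (1 − L)^(1/12) = (0.938)^(1/12) = 0.995, so 2.00 becomes 1.99.
- On the log scale this is 0.0053, and 0.0053/0.235 = 2.3% of the planned half-width.
- With d = ln(1 − L), the width factor is √{[σ² + d²(11/12)(2/3)/22]/σ²} = 1.001.
- The same loss in Treatment Period 1 raises both ratios by 0.5%.

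**Range under other absorption assumptions.** The documents do not give the release or absorption duration of the capsule.

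| Assumption | Unabsorbed at 4 h | Ratio factor, one of 12 |
|---|---|---|
| Zero-order release ending at the peak | about 0% | 1.00 |
| First-order, documented inputs | 6.2% | 0.995 |
| Absorption-limited (ka = 0.0533, ke = 0.695) | 80.8% | 0.87 |

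The last two rows assume that vomiting expels everything not yet absorbed, so each is an upper limit within its model.

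**If the cutoff were read as earlier than 4 h.** No tmax is given for the other analytes, so 1, 2 and 3 h are assumed from the sampling schedule ("at 30 minutes and 1, 1.5, 2, 3, 4, 5, 6, 8, 10, 12, 24, 36, 48, 72 and 96 hours post-dose"). On the first-order model 49.9%, 24.9% and 12.4% would remain, with ratio factors of 0.944, 0.976 and 0.989. That requires verinurad data to be judged by another analyte's peak.

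**Cost of excluding instead.** In the planned model (treatment and subject as fixed effects), the variance multiplier of a treatment difference is 2/12 = 0.1667 with complete data. With one profile missing it is 2/12 + 3/(12 × 11 × 2) = 0.1780 for the affected comparison. Residual degrees of freedom fall from 22 to 21, so the 90% quantile rises from 1.7171 to 1.7207. The width factor is √(0.1780/0.1667) × 1.7207/1.7171 = 1.036. With 14 subjects it is 1.030. A missing Treatment Period 1 profile widens both comparisons by this amount.

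**What the text supplies.** The second listed ground is specific to analyte and period, so reading the first the same way is natural, and 4 h is the only peak time the document states. Late vomiting can be taken up as an event under the mandatory clause. Section 11.2.3 lists exclusions with reasons, Section 11.3 settles the analysis sets at a data review meeting before hard lock, and Section 11.2.1 allows additional analyses, to be described in the CSR.

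**The case for a change.** The strongest opposing case is that no separate SAP is planned (Section 11.2.1), so Section 11.1.3 is the operative text, and it neither names the analyte nor mentions vomiting after the median. The mandatory clause does not define an event. The sponsor's PK guideline is cited in Section 10.2.2 for parameter calculation, not for exclusions. A pre-stated rule would cost only wording, and vomiting times are already captured as adverse event start times.

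The omission is real, and so is the uncertainty about release duration: under absorption-limited kinetics a single case could lower a ratio by up to 13%. However, Section 1.1.1.1 gives a terminal half-life of 13 h with normal renal function and 21 h with moderate impairment. A terminal slope that changes with renal function points to elimination, not absorption, as the slow step. This is not proof, because the same section reports little unchanged verinurad in urine.

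The obvious replacement, a compulsory exclusion window long enough to cover extended release, has its own drawback. On the documented inputs it would discard nearly complete profiles and lose more precision than keeping them. No frequency of late vomiting is documented, so no expected gain can be shown to offset that loss.

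**Conclusion.** The wording lacks detail, but analysts can fill the gap sensibly from the same section, and the claim that the primary AUCs go unprotected is not shown. On the documented 4 h peak and 13 h half-life, with first-order absorption, about 94% of the dose is in by the cutoff. The worst single case among 12 subjects moves a ratio of 2.00 to 1.99, which would not alter its interpretation. A compulsory window would be a trade-off with no demonstrated gain: 3.6% wider for the affected interval, against 0.1% if the profile is kept.

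The conclusion rests on three assumptions: the median is read as that of the analyte in question, absorption is not the rate-limiting step, and late vomiting is considered at the pre-lock review under the general clause. A comparison with and without an affected profile is already open to the sponsor. No change to the plan follows.

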11.2. Methods of Statistical Analyses

11.2.1. General Principles

The statistical methodology below describes the statistical analysis as it is foreseen when the study is being planned.

If circumstances should arise during the study rendering the analysis inappropriate, or if in the meantime improved methods of analysis should come to light, different analyses may be performed. A separate SAP will not be written for the study. Any deviations from the statistical methodology defined in this protocol, reasons for such deviations and all alternative/additional statistical analyses that may be performed will be described in the CSR. Such changes to analyses may be written into an abbreviated SAP, if appropriate. The verification and review of all statistical modeling assumptions will be documented appropriately.

All original and derived parameters as well as demographic and disposition data will be listed and described using summary statistics. All safety data (scheduled and unscheduled) will be presented in the data listings.

Demographic and baseline data will be summarised overall for all dosed subjects. Pharmacokinetic data will be summarised by treatment. Safety and tolerability data will be summarised by treatment period, if applicable.

Frequency counts (number of subjects [n] and percentages) will be made for each qualitative variable. Descriptive statistics for safety data (n, mean, SD, median, minimum and maximum) will be calculated for each quantitative variable (unless otherwise stated). Descriptive statistics will only be presented if n > 3. If no subjects have data at a given time point, then only n=0 will be presented. If n < 3, only the n, minimum, and maximum will be presented. If n=3, only the n, minimum and maximum will be presented; the other descriptive statistics will be left blank.

The following rules will apply to any repeated safety assessments occurring within each treatment period:

- If the repeated measurement of a specific parameter occurs prior to IMP administration (Day 1), then the last obtained value prior to dosing will be used in the descriptive statistics and in the calculation of changes from baseline;
- If the repeated measurement of a specific parameter occurs after IMP administration (Day 1), then the first (non-missing) value after dosing will be used in descriptive statistics and in the calculation of changes from baseline.

The planned sequence for measurement of multiple assessments at the same time point is described in Section 3.1.1.

For safety assessments performed at screening and the follow-up, the following rules will apply for any repeated assessments:

- If the repeated assessment occurs at screening the last available value will be used in the summary statistics;
- If the repeated assessment occurs at the Follow-up Visit the first non-missing assessment will be used in the summary statistics.

All statistical analyses and production of tables, figures and listings will be performed using SAS® version 9.3 or later.

11.2.2. Missing Data

Missing dates and times in the AE data will be handled as described in Section 10.1.1. Concentrations that are non-quantifiable (NQ) in the PK data will be handled as described in Section 11.2.6.

There will be no imputations of other missing data. All subjects will be included into the safety analyses as far as the data permit.

11.2.3. Subject Characteristics

An enrollment listing will be presented and include each subject's full enrolment number and the country where the Clinical Unit is located.

Subjects and/or data excluded from the PK analysis set will be listed including the reason for exclusion. Subject disposition will be summarised and will include the following information: number of subjects enrolled and dosed, number and percentage of subjects completing each ttreatment period of the study and the number and percentage of subjects who were withdrawn (including reasons for withdrawal). Disposition data will be presented based on all dosed subjects.

Subject discontinuations will be listed including the date of study exit, duration of treatment and reason for discontinuation. A listing of ICF response will also be presented.

11.2.3.1. Demographic and Baseline Data

Demographic variables (age, gender, race, ethnicity, height, weight and BMI) will be listed by subject. Demographic characteristics (age, gender, race and ethnicity) and subject characteristics (height, weight and BMI) will be summarised overall. The denominator for percentages will be the number of all subjects dosed.

Medical history data will be listed by subject including visit, description of the disease/procedure, MedDRA SOC, MedDRA PT, start date and stop date (or ongoing if applicable).

11.2.4. Prior and Concomitant Medication and Drug Administration

11.2.4.1. Prior and Concomitant Medication

Prior medications are those that started and stopped prior to the first dose of IMP; all medications taken after first dosing are considered as concomitant (including medications that started prior to dosing and continued after). Prior medication started within 3 months prior to the first dose of IMP will be recorded also in the concomitant medication module of ClinBaseTM.

Prior and concomitant medication will be listed by subject and will include the following information: reported name, preferred term, the route of administration, dose, frequency, start date/time, duration and indication. Prior and concomitant medication will be coded according to the AstraZeneca dictionary.

The duration of medication use will be calculated as:

Duration = end date/time - start date/time + 1

The duration may be presented in hours or days in the listing depending on the applicability to the emerging data. For medications with partial or completely missing start date/times and/or end date/times, the duration will not be calculated.

Medications with missing or partial start date/time and/or end date/time such that it is not possible to classify as prior or concomitant will be considered as concomitant in the listings.

11.2.4.2. Drug Administration

Drug administration dates and times will be listed for each subject and treatment period.

11.2.5. Safety and Tolerability

All safety data (scheduled and unscheduled) will be presented in the data listings. Continuous variables will be summarised using descriptive statistics (n, mean, SD, minimum, median, maximum) by treatment. Categorical variables will be summarised in frequency tables (frequency and proportion) by treatment. The analysis of the safety variables will be based on the safety analysis set.

Adverse events will be summarised by PT and SOC using MedDRA vocabulary. Furthermore, listings of SAEs and adverse events that led to withdrawal will be made and the number of subjects who had any AE, SAEs, AEs that led to withdrawal, and AEs with severe intensity will be summarised. Adverse events that occur before dosing will be reported separately.

Tabulations and listings of data for vital signs, clinical laboratory tests and ECGs (listings only) will be presented. Any new or aggravated clinically relevant abnormal medical physical examination finding compared to the baseline assessment will be reported as an AE. Data will

be summarised for the observed values at each scheduled assessment, together with the corresponding changes from the baseline when baseline is defined. Clinical laboratory data will be reported in Système International units in the CSR.

Out-of-range values for safety laboratory will be flagged in individual listings as well as summarised descriptively using agreed standard reference ranges and/or extended reference ranges (eg, AZ, program, or laboratory ranges).

11.2.6. Presentation of Pharmacokinetic Data

A listing of PK blood sample collection times, as well as derived sampling time deviations and all reportable concentrations will be presented for verinurad, M1, M8, allopurinol, and oxypurinol for all dosed subjects. An additional listing of PK concentrations versus time will be presented for those analytes based on the PK analysis set.

Plasma concentrations will be summarised for the PK analysis set for each time point by treatment period for each analyte separately using CSP scheduled times and appropriate descriptive statistics.

Further details on presentation of PK concentration and parameter data will be presented according to the most recent version of the AZ CPE TFL standards, that includes applicable descriptive statistics, handling of individual concentrations below the LLOQ for listings, descriptive statistics and figures, and precision and rounding rules for concentrations and PK parameter data.

Individual concentrations with time deviations of greater than $\pm 10\%$ from the CSP scheduled time will be used in the PK analysis but will be flagged for exclusion from the summary tables and corresponding figures.

Individual plasma concentrations versus actual elapsed time after dose will be plotted on both the linear and semi-logarithmic scale with the test and reference treatments overlaid on the same plot and separate plots for each subject and analyte. Plots will be based on all dosed subjects.

Combined individual plasma concentration versus actual times will be plotted based on the PK analysis set on both the linear and semi-logarithmic scale, with all subjects for the same treatment overlaid on the same plot and separate plots for each treatment and analyte.

Gmean (+/- gSD) plasma concentration versus nominal sampling time will be plotted on both the linear scale and semi-logarithmic (no gSD presented) with all treatments overlaid on the same plot and separate plots for each analyte. Plots will be based on the PK analysis set. Focus plots may be provided if there will be no clear distinction among profiles.

